Mechanisms of Change in Yoga and Physical Activity for Veterans

NCT03509909

August 16, 2022

Background and Significance

Posttraumatic stress disorder (PTSD) is a chronic, debilitating disorder that broadly impacts the life of affected individuals. Existing treatment approaches have clinically meaningful positive effects on PTSD symptoms, yet the majority of patients who receive our best treatments continue to have a diagnosable disorder after treatment (Steenkamp, Litz, Hoge, & Marmar, 2015), pointing to the need for more robust recovery plans. Clinically significant residual PTSD symptoms and individual preferences have led many patients seek alternatives to psychotherapy and pharmacotherapy (Clarke, Black, Stussman, Barnes, & Nahin, 2015). Consequently, VA facilities currently offer a wide array of complementary and alternative approaches (Libby, Pilver, & Desai, 2012), despite a paucity of evidence about their effectiveness for the treatment of PTSD ([name], Strauss, & Schnurr, 2016). Current empirically-supported therapies emphasize habituation of fear/arousal and change in dysfunctional beliefs about the trauma (e.g., Schumm, Dickstein, Walter, Owens, & Chard, 2015). PTSD, however, is also characterized impaired emotion regulation (Seligowski, Lee, Bardeen, & Orcutt, 2015) and cognitive processing deficits ([name] & [name], 2015), suggesting additional mechanisms by which PTSD may be addressed. *An intervention that reduces barriers to care, complements current first-line approaches, and/or targets mechanisms that maintain PTSD may ameliorate the broad range of negative effects of this disorder; yoga may accomplish all of these.* The acceptability of yoga is readily apparent. It is widely offered within VA PTSD programs (Libby, Reddy, Pilver, & Desai, 2012), and surveys suggest that interest in yoga continues to grow, with over 30 million Americans engaged in some type of yoga practice (Ipsos Public Affairs, 2016). We argue herein that yoga potentially impacts transdiagnostic mechanisms that are not only connected to the etiology and maintenance of PTSD but also may increase one's ability to tolerate trauma-focused psychotherapy.

The two largest randomized controlled trials of yoga for civilian PTSD suggest that the practice leads to meaningful change in PTSD symptoms from pre- to post-treatment; in both cases this effect was greater than the control condition with effect sizes in the range of 1.07-1.65 (Jindani, Turner, & Khalsa, 2015; van der Kolk et al., 2014). Although these two trials suggest optimism, the broader literature on yoga for PTSD is highly variable and of inconsistent quality, thus limiting the conclusions that can be drawn. Several studies show no difference between yoga and a control condition (e.g., Mitchell et al., 2014; Thordardottir, Gudmundsdottir, Zoega, Valdimarsdottir, & Gudmundsdottir, 2014), and one very small study found negligible effect on PTSD symptoms among Veterans (Staples, Hamilton, & Uddo, 2013). Whereas methodology may be one factor in the variability in outcomes observed in yoga studies, another likely source is the fact that yoga practice varies widely, ranging from quite vigorous to highly relaxing and including no to heavy emphasis on physical asanas (postures), meditative practices, spirituality or breath control. *Just as trying to establish whether or not "psychotherapy" is effective for PTSD would be untenable because of the broad range of procedures encompassed by that term, it is unlikely that "yoga" will be proven efficacious or not. The quest for effective psychotherapeutic strategies was driven by a conceptual understanding of processes that create or maintain psychopathology and the use of techniques to modify those mechanisms. Similarly, we suggest that delivering efficacious yoga-based interventions will depend on understanding mechanisms of change and targeting those variables in the therapeutic teaching of yoga.*

Accordingly, the **primary aim** of this randomized clinical trial is to examine the efficacy of a manualized hatha yoga protocol as compared to a supportive physical activity control in a sample of Veterans with PTSD, thus adding to the evidence base in this understudied area. The proposed study incorporates "gold standard" requirements for PTSD treatment trials, including clearly defined target symptoms; reliable and valid measures; use of blind evaluation of outcome; systematic assessor training; manualized, replicable, specific treatment programs; unbiased assignment to condition; and measurement of treatment adherence (Foa & Meadows, 1997). The larger published and ongoing trials of yoga have used wait list, group health education and psychotherapy as control conditions, but none have addressed the important question of whether or not yoga confers more benefit than other types of physical activity; this project answers that need. The yoga literature continues to develop, with recent work showing positive clinical effects when applying Trauma Sensitive Yoga for women (Kelly et al., 2021). This project will contribute to the literature by examining a more typical hatha yoga practice in a diverse sample.

A **secondary aim** of this project is to understand the mechanisms by which clinical change may occur when Veterans with PTSD practice yoga. *This aspect of the study extends our current knowledge as there is no comprehensive model of yoga's impact on PTSD.* Out of this understanding, we envision developing guidelines for the therapeutic application of yoga. Given the tens of thousands of people teaching yoga (Bachman, 2015) and the wide range of settings in which Veterans may practice, trying to disseminate a particular protocol may be infeasible. More realistically, we would aim to extend current trauma-sensitive yoga

[figure not shown]
guidelines, which focus largely on the acceptability of the practice (Emerson, Sharma, Chaudhry, & Turner, 2009), to highlight key principles and postures that support recovery. In doing so, we could create a consumer's guide for yoga for PTSD so that Veterans can apply yoga to work on key concepts wherever they choose to practice. *In doing so, we would greatly enhance the disseminability of effective yoga practice.* Further, we believe that this work has the potential to inform the application of yoga to other mental health conditions, as the mechanisms we propose to examine have applicability to other disorders.

Mechanisms of change. Proposed herein are two models through which yoga may impact PTSD: the attention model and the coping model. These transdiagnostic concepts have well-established links to psychopathology, and some early evidence that they may be modifiable through yoga. Thus it is an important next step to determine whether attentional functioning and coping are modified through yoga practice and whether these changes explain observed clinical benefits.

Attention model. PTSD is characterized by deficits in aspects of cognitive processing. Compared to individuals without a psychiatric diagnosis, those with PTSD demonstrate specific deficits in attention and executive function (Vasterling & Brailey, 2005). These deficits are observed both when individuals are required to utilize cognitive processes in the context of neutral information (e.g., Falconer et al., 2008) and emotionally-valenced information (e.g., disengaging attention from threat stimuli; Pineles et al., 2009), and may correspond to subjective symptoms observed in the disorder (e.g., hypervigilance, cognitive avoidance, concentration difficulties; Upperville et al., 2011). Neurobiologically, individuals with PTSD demonstrate hypoactivation of prefrontal cortical regions that underlie performance on complex attention and executive function tasks (e.g., dorsolateral prefrontal cortex, anterior cingulate, ventromedial prefrontal cortex; Falconer et al., 2008; Francati, Vermetten, & Bremner, 2007).

Yoga frequently involves active and deliberate regulation of attention to a fixed point (known as a *drishti*), which creates a focused attention mindfulness practice (Lutz, Slagter, Dunne, & Davidson, 2008). Both studies of expert meditators and of training in novices show that focused attention mindfulness is linked to enhanced attentional functioning (e.g., Lutz et al., 2008; Moore & Malinowski, 2009), leading to a “significant decrease in emotionally reactive behaviors that are incompatible with stability of concentration” (Lutz et al., 2008, p. 3). Such findings drive the suggestion that this aspect of yoga practice drives cognitive benefits above and beyond the benefits of physical exercise (Gothe & McAuley, 2016). Empirical studies across diverse samples (e.g., older adults, children, patients with multiple sclerosis, patients with schizophrenia) also demonstrate yoga's beneficial effects on cognition as assessed using objective cognitive assessment batteries (e.g., Hariprasad et al., 2013). The cognitive systems utilized to hone focused attention are likely the same systems that govern cognitive performance more broadly speaking; thus, yoga may improve more global cognitive indices by way of enhancing performance and efficiency of attention (Gothe, Kramer, & McAuley, 2014; Gothe & McAuley, 2016). Work in our lab recently showed that a computer-based attentional control training successfully reduced reexperiencing symptoms with a medium-large effect size ([name], Stein, & [name], 2015). As depicted in Figure 1, we will examine a multiple mediation model (Wang et al., 2012), whereby one mediator (mindfulness) can affect the other (attentional control). Thus, we will examine the model that yoga increases mindfulness, which increases attentional control, which in turn reduces PTSD symptoms. We will compare the fit of this model to the models including only one of these mediators, i.e., mindfulness mediates the relationship between yoga and PTSD symptoms and attentional control mediates the relationship between yoga and PTSD symptoms.

Figure 1: Path diagram for the multiple mediation model of attentional control and mindfulness

[figure not shown]
Work in our lab recently showed that a computer-based attentional control training successfully reduced reexperiencing symptoms with a medium-large effect size ([name], Stein, & [name], 2015). As depicted in Figure 1, we will examine a multiple mediation model (Wang et al., 2012), whereby one mediator (mindfulness) can affect the other (attentional control). Thus, we will examine the model that yoga increases mindfulness, which increases attentional control, which in turn reduces PTSD symptoms. We will compare the fit of this model to the models including only one of these mediators, i.e., mindfulness mediates the relationship between yoga and PTSD symptoms and attentional control mediates the relationship between yoga and PTSD symptoms.

Coping model. Distress following exposure to trauma is a normal human experience that typically fades with the passage of time. Current models of PTSD suggest that one factor that drives the development and maintenance of the disorder (i.e., normal distress does not resolve) is pathological coping. Consistent with this, a recent meta-analysis of 57 studies showed that strategies such as rumination, thought suppression and experiential avoidance are strongly associated with PTSD (Seligowski, Lee, Bardeen, & Orcutt, 2015). There is evidence to suggest that yoga and other focused meditation approaches reduce the use of such maladaptive coping strategies. A recent pilot study of yoga (vs assessment only control) in women found that yoga was associated with reduced suppression of emotion, although this the change was not associated with change in

PTSD symptoms in this small sample ($n = 38$; Dick, Niles, Street, DiMartino, & Mitchell, 2014). Such mediation has been observed, however; focused meditation as compared to relaxation and wait list was associated with increased use of effective emotion regulation strategies, which, in turn, correlated with reduced trait anxiety (Menezes & Bizarro, 2015). Mindfulness meditation as compared to a relaxation control was associated with decreased use of distraction and rumination; change in rumination partially mediated observed changes in distress (Jain et al., 2007). Thus, yoga may reduce PTSD symptoms by directly reducing maladaptive coping (refer to Figure 2).

Yoga may also support positive coping by increasing tolerance of discomfort. Yoga provides physical experiences in which to learn non-reactivity. For example, yoga differentiates between pain and discomfort such that pain signals the need to respond (e.g., withdrawing a hand from a hot surface) whereas discomfort does not (e.g., remaining in an uncomfortable situation and simply observing one's reaction). This increased capacity has been demonstrated experimentally. For example, individuals with a long history of yoga practice were able to tolerate induced pain in the laboratory setting about twice as long as controls without a yoga practice (Villemure, Ceko, Cotton, & Bushnell, 2014). Thus, we suggest that yoga can change one's tolerance of discomfort.

Figure 2: Path diagram for the multiple mediation model of tolerance of discomfort and coping

Tolerance of discomfort has been described in multiple ways in the literature and has been associated with PTSD. The term “distress tolerance” is used to describe the ability to tolerate uncomfortable emotions (Simons & Gaher, 2005). Distress tolerance inversely correlates with PTSD severity; specifically, those with poorer distress tolerance have more re-experiencing symptoms and emotional numbing (Vujanovic et al., 2013). The idea that increased tolerance of discomfort may ameliorate PTSD is supported by studies of “anxiety sensitivity (AS),” which is the fear of anxiety symptoms (physiological, cognitive and social). AS is not only related to the development and maintenance of the PTSD ([name], Kennedy, & Stein, 2002), but change in AS predicts change in PTSD symptoms. Further, interventional studies show that reducing AS ameliorates PTSD (Allan, Short, Albanese, Keough, & Schmidt, 2015). Further, Medina et al. (2015) showed that hatha yoga increased distress tolerance (specifically an aspect of distress tolerance called distress absorption), which led to more adaptive coping (namely less emotionally-driven eating in response to stress). A direct extension of these data is a multiple mediation model for PTSD involving tolerance of discomfort and coping, as diagrammed in Figure 2. We will examine the model that yoga increases tolerance of discomfort, which improves coping, which in turn reduces PTSD symptoms. We will compare the fit of this model to the models including each of the mediators alone. To inform future work, we additionally will explore whether any combination of the Attention and Coping Models explains more variance than either one alone.

Summary. In light of the evidence presented, we predict that yoga will be associated with clinically significant change in PTSD symptoms and that the change associated with yoga will be significantly greater than the change associated with physical activity because of the meditative nature of the practice. We will secondarily assess the impact of the two interventions on symptoms that are commonly associated with PTSD and examine the clinical utility of both interventions (Smart, 2006) with the ultimate goal of guiding the clinical application of the practice. Further, we have described two models that link yoga practice to change in PTSD symptoms. The fit of the proposed Attention and Coping Models will be assessed and compared.

Yoga is a highly popular practice, which is increasingly being leveraged as a part of Veterans' PTSD recovery programs. Although initial evidence suggests the usefulness of this strategy, it is urgent that we gather more evidence as to its efficacy for Veterans and understand its mechanisms of action. Such information is critical if we are to find ways to replicably deliver yoga to Veterans for symptom management. By focusing on key mechanistic variables that are linked to the development and maintenance of PTSD and are impacted by yoga, we believe that we will be able to identify pathways to change. This information, in turn, can be used to optimize practice and create delivery guidelines. This project therefore represents an important next step in yoga intervention research.

Preliminary Studies and Current Status of the Field

We relied on three primary sources of preliminary information in designing the proposed study: clinical data from ongoing yoga groups at a VA San Diego, ongoing and past studies at our facility of yoga and other complementary interventions, and extant literature on yoga for PTSD.

Acceptability

Clinical data supports the acceptability of yoga for PTSD among Veterans at this facility. There has been a “Yoga, Nutrition and Meditation” group for “pain and suffering” at the Oceanside Community Based Outpatient Clinic since 2015. Offered in 8-week group meetings, the group features gentle hatha yoga with some adaptations for physical limitations (e.g., availability of seated poses). In FY 16, 66 unique Veterans took advantage of this offering, accounting for 330 visits. In FY17 to date, there have been 53 unique participants with a total of 294 encounters. Thus, patients on average are completing 5-6 of the 8 sessions.

Successful past research also speaks to the acceptability yoga and similar complementary approaches in San Diego. Co-Investigator [name] has been conducting yoga research at VA San Diego since 2004, establishing the feasibility of conducting yoga research at this facility. [name] most recent RCT of yoga for VA patients with chronic low back pain easily enrolled the target of 150 VA patients within 30 months (Groessl et al., 2017). This study, which utilized the protocol to be used herein, compared hatha yoga delivered immediately or after a delay. Participants attended an average of 13 (median 15) of 24 classes, and 80% were retained at 6- and 12-weeks, with 73% retention at 6-months. Both groups showed significant change on the primary outcome measure, the Roland-Morris Disability Questionnaire. Mental health outcomes were not measured in this study, but [name] past work with pain patients showed significant change in depression and mental health related quality of life (Groessl, Weingart, Aschbacher, Pada, & Baxi, 2008).

The acceptability of a yoga and physical activity trial is also suggested by successful trials at this facility utilizing other complementary and alternative treatments for PTSD. [name] recently completed a feasibility and proof of concept study of compassion meditation (CM) for Veterans with PTSD. CM focuses on the heartfelt wish that others be free of suffering based on cultivation of a common sense of humanity. This NCCIH R34 (PI [name]) involves iterative refinement of the meditation protocol based on quantitative and qualitative data followed by a small randomized controlled trial comparing CM to a relaxation-based control. Pooled data from the nonrandomized refinement phase, which enrolled 36 participants in 4 groups, shows meaningful change in PTSD (partial eta squared = 0.27) and depression (partial eta squared = 0.19). The subsequent randomized pilot study enrolled 38 participants in CM or a relaxation condition; results are not yet available. [name] was also a co-investigator on [name] mantram repetition trials. The first enrolled 66 Veterans with PTSD in a group format (Bormann, Liu, Thorp & [name], 2012), and the second enrolled 118 Veterans in a randomized trial that delivered care one-on-one (manuscript submitted for publication). Finally, [name] recently randomized 203 Veterans with PTSD to Transcendental Meditation, Prolonged Exposure or health education (personal communication).

Thus, the successful track record of implementing clinical and research programs using complementary approaches at the VASDHS, is strong evidence for the acceptability of this type of study at this facility.

Feasibility

Although we initially projected being able to enroll approximately 6 Veterans per month in the trial for a sample of 144 completers, this has not proven to be realistic. In 38 months of active recruitment, we have screened 326 individuals (~9/month) of whom 51% consented to participation and 26% were randomized (~2.5/month). We believe that these lower-than expected rates of participation and randomization are partly related to competition with many other opportunities to engage in recorded or live-streamed yoga/exercise classes. As a result, we plan to enroll approximately 96 Veterans in the trial (48/group).

Pilot Effect Sizes

Effect sizes in studies of yoga for PTSD vary widely (0.08 to 1.65; Wells, [name], Schmalzl, Groessl, & Strauss, 2016), perhaps because of variability in practice types and the populations studied. The largest randomized controlled trial of yoga for PTSD to date compared a “trauma sensitive” version of Kundalini yoga to a wait list control in an 80-person civilian sample (Jindani et al., 2015). Greater decreases in PTSD symptoms (Cohen’s $d = 1.65$), insomnia, stress and anxiety were observed in the yoga group. In addition, yoga was associated with increased in positive affect and resilience. No significant changes in depression or negative affect were observed. This trial is limited, however, by the lack of an active control and a high rate of

attrition. It's generalizability to Veterans is also unknown. The other relatively large randomized evaluation of yoga included 64 women with chronic, treatment-resistant PTSD (van der Kolk et al., 2014). As compared to a health-education class, yoga was associated with greater change in PTSD symptoms (Cohen's $d = 1.07$). It is unknown, however, how these findings generalize to men. One uncontrolled trial involved Kripalu yoga, a form of hatha yoga, for active duty and Veteran participants. They observed large effect size pre-post change in symptoms (Cohen's $d = .77$), although this change was less than a benchmark that the authors calculated based on meta-analysis of published studies of active PTSD treatments (Johnston et al., 2015). In contrast, smaller studies have found no difference between yoga and a control condition (Mitchell et al., 2014; Thordardottir et al., 2014) or negligible effect on PTSD symptoms in Veterans ($n = 12$; Staples et al., 2013). Weighting the larger studies more heavily, we have powered the study to detect a medium to large effect size.

Ongoing Research

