Innovation. The present study extends and compliments previous yoga research. Much of the current yoga literature is limited by small sample sizes and poor methodological rigor. In response to this need, the proposed study includes a randomized controlled design, with an active control condition that is matched for time/attention, social group interactions, attention, and expectancy. It features standardized and psychometrically sound assessment instruments, including blinded evaluation, and addresses the limited generalizability of previous samples by including both men and women with broad inclusion/exclusion criteria. Finally, it is set in a Veteran population, which is an understudied group in the published literature and may differ in important ways from non-military populations. Furthermore, the yoga intervention is a manualized Hatha yoga, which has been implemented in prior studies at this facility, and is reviewed for fidelity. Thus, the proposed project addresses an important need for high quality studies of yoga for PTSD. *The greatest innovation, however, lies in the evaluation and comparison of the Attention and Coping Models. Examination of these mechanisms will advance our understanding of the way in which a guided asana practice may impact PTSD, but will also inform yoga-based mental health treatment more broadly as these transdiagnostic processes are applicable to other mental health concerns.*

Research Design and Methods

The proposed study is a randomized controlled trial of Hatha yoga as compared to supportive physical activity in Veterans with PTSD. A sample of approximately 96 recruited (refer to Sample Size). Longitudinal outcome assessment will take place over approximately a 6 month period; refer to Table 1 for an overview of measures at each time point. A 3-month follow-up is planned because information about maintenance of change following the completion of a yoga intervention is important given the long-term follow-up data from the van der Kolk trial, which suggest that ongoing practice is critical continued clinical effects (Rhodes, Spinazzola, & van der Kolk, 2016).

Procedures

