Potential participants will be recruited from VA clinics (including primary care and mental health) and the community, following procedures that have been proven successful in our previous meditation and yoga trials. The initial contact for potential participants will be with a study recruiter/assessor, who will complete informed consent and conduct the evaluation for eligibility (see *Assessment*). After eligibility and consent are confirmed, the participant will complete the baseline assessment and then will have brief safety assessments every class; they will be asked to complete a total of 12 classes within 14 weeks. A follow-up will occur 12 weeks after the completion of the final class. No shows will receive a telephone follow-up. Participants will receive a payment for each assessment session (\$50 baseline part 1, \$50 baseline part 2, \$50 post-treatment part 1, \$50 post-treatment part 2, \$50 follow-up part 1, \$50 follow-up part 2 for a total of \$300; refer to Table 1).

Randomization will be done by the study statistician. In the initial phase of the trial, this was a 2:1 allocation to yoga and physical activity and took place at the individual level. Uneven allocation was planned to allow for sufficient power to accomplish the modeling proposed in Aim 2 (refer to *Sample Size*); given pandemic-related difficulties with accrual, however, the allocation will be reversed to 1:3 for the final months of the study to accomplish a minimum of 48/cell. The randomization table will be prepared prior to start of the study and revised for the new allocation strategy. Using an individual randomization strategy and continual group enrollment allows patients to begin treatment more quickly (i.e., as soon as the baseline evaluation is complete), which reduces attrition. This continual enrollment strategy is possible because the yoga and physical activity classes do not build from week to week; rather, every class provides multiple options for each pose/exercise to allow for individual differences, as is consistent with typical practice in the community. Further, sharing of personal information is minimized in this type of class, so newcomers are unlikely to cause discomfort among group members. Further, this strategy may support better retention. By allowing participants 14 weeks in which to complete 12 classes, participants will be able to make up missed classes to receive the full “dose.”

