Sample size. We used the method provided by Hedeker, Gibbons, & Waternaux (1999) for the Random Regression Model and the RMASS program provided by Hedeker (2016) to estimate needed sample size for Aim 1. Medium effect size was selected based on finding from previous yoga trials (Wells et al., 2016) and was defined as a between-group difference increasing linearly from 0 at baseline to .5 SD units at the last time point. The minimum power estimation is based on sample size calculation for 10% and 20% attrition, correlations of 0.2, 0.5, and 0.8 between the repeated measures, and for medium and large effect sizes. We are confident that with the proposed total sample size of at least 48/arm would be sufficient to achieve a minimum 80% power for the primary aim.

Management

Management of this single-site study will be [name] responsibility. She has considerable experience in research management from small developmental grants (e.g., NCCIH R34) to a large multi-site consortium (INTRuST PTSD/TBI Clinical Consortium Deputy Director) and center of excellence (VASDHS CESAMH Associate Director). Administrative aspects of the project will be supported by [name], who has been [name] lead coordinator for more than a decade. [name] will coordinate scientific aspects of the project, holding regular meetings with the investigative team. [name], the study biostatistician, will work closely with [name] around data management and analysis. [name] will draw on his experience with yoga research to help with issues of recruitment, enrollment and retention. Drs. [name] (attention) and [name] (pain) will provide guidance in their relative areas of expertise. [name], who is a licensed clinical psychologist, also will be responsible for clinical oversight. The timeline of major study activities is presented in Table 2.

Table 2. Study Timeline

Year 1 (2018-2019)	Year 2 (2019-2020)	Year 3 (2020-2021)	Year 4 (2021-2022)	Year 5 (2022-2023)
Original Timeline				

Set-up	Recruitment (approx. 6/month x 30 mos)	Follow-up, data lock	Dissemination	Analyses	
Regulatory	Assessment				
Hiring	Intervention delivery, fidelity (12 groups)				
Training	Data management				
Recruitment	DSMB reporting				
Revised Timeline					

 ✓ Set-up ✓ Regulatory 	
 Recruitment (approx. 6/month x 30 mos) Assessment Intervention delivery, fidelity (12 groups) Data management DSMB reporting 	Follow-up, data lock	Dissemination	Analyses	

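### If the roughly 85 already randomised were allocated 2:1, a total of 96 gives about 59/37, not 48/48; 48 controls need about 111

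*Combined protocol and SAP*

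**What the plan says.** Preliminary Studies, Feasibility, describes accrual: "In 38 months of active recruitment, we have screened 326 individuals (~9/month"; of these, "51% consented to participation and 26% were randomized (~2.5/month". It abandons the former target, which was "for a sample of 144 completers", and replaces it: "we plan to enroll approximately 96 Veterans in the trial (48/group". The opening of Research Design and Methods repeats the total: "A sample of approximately 96 recruited".

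Procedures gives the allocation history. In the initial phase "this was a 2:1 allocation to yoga and physical activity"; now "the allocation will be reversed to 1:3 for the final months of the study to accomplish a minimum of 48/cell". Sample size, in the Analytic Plan, rests its claim of at least 80% power for the primary aim on "the proposed total sample size of at least 48/arm".

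Nowhere does the plan give the number randomised to each arm, the number randomised when the ratio changes, or a total worked out from the two ratios.

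**The concern.** A trial that has randomised most of its patients 2:1 cannot end balanced at a total only slightly above the present count. On the stated figures the yoga arm has probably already passed 48, so each further yoga patient moves a total of 96 further from 48/48.

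The total of 96 and the floor of 48 per arm therefore appear to be two different targets. They imply different end dates and different control arms, and the plan has no explicit criterion for ending recruitment. The power statement is tied to the per-arm figure, so if recruitment ends at 96 that statement describes arms the trial will not have. It is also unclear whether 96 and 48 count patients randomised or patients completing, because the target they replace was expressed in completers.

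**Working it through.** **Inputs.** 326 screened, 38 months, 26% randomised, about 2.5 randomised per month, total 96 (Feasibility); ratios 2:1 then 1:3, yoga to physical activity (Procedures); at least 48 per arm, attrition 10% and 20%, medium effect 0.5 SD (Sample size).

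**The plan's own figure.** 48 + 48 = 96 is correct as addition. The question is whether the allocation delivers it.

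**Randomised to date.** 0.26 × 326 = 84.8 (83.1 to 86.4 if 26% is rounded from 25.5–26.5%). Rate: 84.8/38 = 2.23 per month.

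**Formula.** With n randomised at 2:1 and the rest of N at 1:3:
- yoga = (2/3)n + (1/4)(N − n)
- physical activity = (1/3)n + (3/4)(N − n)

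**Stopping at N = 96 with n = 84.8.**
- At 2:1 so far: 56.5 / 28.3.
- Places left: 96 − 84.8 = 11.2, which at 1:3 add 2.8 / 8.4.
- Final arms: **59.3 / 36.7** (58.6/37.4 to 60.0/36.0 over the rounding of 26%).
- All 11.2 places to control: 28.3 + 11.2 = 39.5 (38.4 to 40.6 over the rounding).
- If randomisation is simple (unblocked), with 85 at 2:1 and 11 at 1:3, the chance of at least 48 controls at 96 is about 0.9%.

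**Reaching 48 controls.** (48 − 28.3)/0.75 = 26.3 more, so N = **111.1** (110.2 to 112.0), with arms about 63/48. At 2.23 per month that takes 26.3/2.23 = 11.8 months, against 11.2/2.23 = 5.0 months to reach 96.

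**Switch point that would make 96 work.** (2/3)n + (1/4)(96 − n) = 48 gives n = 57.6. The ratio would then have been 1:3 for (84.8 − 57.6)/2.23 = 12.2 of the 38 months already counted.

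| Randomised before switch | Arms at 96 (yoga/control) |
|---|---|
| 58 | 48/48 |
| 65 | 51/45 |
| 70 | 53/43 |
| 75 | 55/41 |
| 80 | 57/39 |
| 85 | 59/37 |

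**Other readings of the count.**
- From the stated rate, 2.5 × 38 = 95 randomised: 96 gives about 64/32, and 48 controls need about 117.
- 26% taken of consenters: 0.51 × 326 × 0.26 = 43 randomised, or 1.1 per month, which contradicts the stated rate; 96 then gives 42/54, still not 48/48.

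**If 96 means completers (n = 85).**
- 10% attrition: 96/0.9 = 106.7 randomised, arms 62.1/44.6, completers 55.9/40.1.
- 20% attrition: 96/0.8 = 120 randomised, arms 65.4/54.6, completers 52.3/43.7.
- 48 control completers need 85 + (53.3 − 28.3)/0.75 = 118 randomised at 10% attrition, or 85 + (60 − 28.3)/0.75 = 127 at 20%.

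**Power.** Two-mean normal approximation, d = 0.5, two-sided 0.05, no attrition: 48/48 gives z = 0.5 × √(48 × 48/96) = 2.449, power 68.8%; 59/37 gives z = 0.5 × √(59 × 37/96) = 2.384, power 66.4%. A slope comparison with a difference growing linearly to 0.5 SD over three or four assessments, correlations 0.2, 0.5 and 0.8, and attrition 0 to 20% gives quite different absolute levels. The loss from 48/48 to 59/37 is at most about 2.5 points throughout.

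**The case against.** The strongest reply is that the deciding input is missing. The plan reports neither arm counts nor the switch point, and 48/48 lies at one end of the table above. The inference that the 85 were allocated 2:1 rests largely on tense, past for 2:1 and future for 1:3, and the document keeps other outdated tenses: the randomisation table is still to be prepared before the study starts. This stands as a limit on certainty. It does not rescue the figure, because a switch at about 58 means roughly a year of 1:3 already completed and about 5 months more to come, which fits poorly with a change described as belonging to the last months.

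Second, the per-arm figures are floors that a total near 111 would satisfy, and the stated purpose of the ratio change points to the floor as the real target. That is fair, but then the total of 96, given in two places and once with 48 per group beside it, is wrong and should go.

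Third, on a completers reading heavier attrition closes the gap. At the 73% six-month retention reported for the facility's back-pain yoga trial, 96 completers would be about 50/46; at 68% retention, 48/48. Those need 96/0.73 = 132 and 96/0.68 = 141 randomised, some 47 to 56 more than now, or about 21 to 25 months at 2.23 per month.

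Fourth, the consequence is modest: the mixed model does not need equal arms, and the two-mean power figures are not the planned RMASS calculation, so they cannot be set directly against 80%. Both points stand and limit the weight of the concern.

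**Conclusion.** The concern holds. On the best reading of the text, with about 85 randomised at 2:1, ending at 96 leaves about 59 in yoga and 37 in physical activity, 11 below the stated floor. Meeting the floor takes about 110 to 112. The conclusion rests on 26% being a share of the 326 screened and on the switch not yet having happened. It weakens steadily as the switch is moved earlier and vanishes only at about 58. Using the stated 2.5 per month instead makes the shortfall worse.

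The effect on power is small. What matters is that the plan states a size its allocation does not deliver and leaves open which target ends recruitment, a difference of about 15 randomisations and 7 months. It should be corrected, with medium confidence because the actual arm counts are not shown.

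**What to change.** 1. In Feasibility and Procedures, report the actual number randomised to each arm at the change to 1:3, and reconcile the 26% with the monthly rate (2.2 versus 2.5).
2. Wherever 96 and 48 appear, say whether they mean randomised or completers.
3. Name one criterion for ending recruitment and give the arm sizes it delivers, computed from the trial's own counts. Two options on present figures:
   - a total of 96 with unequal arms (expected about 59/37), withdrawing the 48-per-cell floor;
   - 48 in physical activity (expected total about 111 to 112, arms about 63/48), withdrawing the 96.
4. Restate power in Sample size on those arms, using the planned method and stating the attrition and correlation assumed.

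The first option is text only: no extra patients, but it gives up the floor and states slightly lower power. The second costs about 15 randomisations beyond 96, about 7 further months at the observed rate. If the counts show that the switch came early enough for 48/48, one sentence giving them settles the matter.
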